Part C is an extension of the study for patients from both Part A and Part B and consists of 2 periods, a 48-week treatment period and a 24-week follow-up period after the last dose of study drug. All patients from Part A who enter Part C will initially receive open-label evinacumab 15 mg/kg IV Q4W. The final dose in Part C will be the same as the dose in Part B; therefore, the dose in Part C could be adjusted to align with the dose in Part B. Patients who are receiving background LMT or who are undergoing apheresis should make every effort to maintain a stable LMT and a stable apheresis schedule (as applicable) throughout the duration of the study to the end of the study. The frequency of apheresis may be reduced during this part of the study based on the investigator's judgement. The Sponsor of this study, consistent with our corporate policy governing access to investigational drugs in confirmatory clinical studies, is committed to provide evinacumab to patients after their participation in this trial has concluded, if permitted per local laws. Agreement to continue treatment beyond this study is a treatment decision that must be made by the investigator, and the patient or their parent/guardian. After completion of the study, investigators interested in continuing treatment with evinacumab in patients considered to have a positive response can discuss post-trial treatment options with the Sponsor, including participation in a CUP or EAP.

Study Duration

For a patient in Part A, the duration of the study is up to approximately 34 weeks, which includes up to an 8-week run-in period, a 2-week screening period, a 16-week open-label treatment and observation period, an 8-week follow-up period (for those patients who decide not to enter Part C). For patients who enter Part C, there will be no follow-up period for Part A and the combined duration of Part A and Part C could be up to 98 weeks, including a 24-week follow-up period after the last dose of study drug in Part C. Although, patients who enter a CUP or EAP may forgo the 24-week follow-up period after the last dose.

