6. STUDY DESIGN

6.1. Study Description and Duration

[figure not shown]
This study consists of 3 parts: Part A, Part B, and Part C

- Part A: phase 1B single arm, single dose PK/PD study
- Part B: phase 3, single-arm, 24-week, open-label efficacy and safety study
- Part C: phase 3, 48-week treatment period and 24-week follow-up period
 - Note, for patients who enter a CUP or EAP, they may forgo the 24-week follow-up period after the last dose. In this situation, the end of treatment (EOT) visit will be their last visit.

Part A is a phase 1B single-dose, open-label study to determine the safety, PK and PD of evinacumab 15 mg/kg IV in approximately 6 patients ages 5 to 11 years with HoFH. To ensure a distribution of body weight within Part A of the study, every effort will be made to enroll 3 patients <25 kg and 3 patients ≥25 kg. Additionally, to ensure a distribution of ages, every effort will be made to enroll 2 patients <10 years of age. All patients who successfully complete Part A may continue receiving evinacumab in Part C. Initially, patients from Part A who enter Part C will receive evinacumab 15 mg/kg IV Q4W. When PK data from all patients in Part A have been sufficiently analyzed, the dose for Part B will be determined using the cumulative data to date with evinacumab and data from Part A. If data from 6 patients is insufficient, up to 4 more patients may be enrolled to confirm the dose in Part B. The dose for Part B will also be the final dose in Part C. The dose for Part B (and final dose in Part C) will likely remain at 15 mg/kg IV Q4W. However, there is a small possibility that the exposure analysis or the observed PD effect indicate a small increase in the dose is needed for the pediatric population to match the exposure and PD effect observed in adult patients. As such, the dose in Part B (and final dose in Part C) could be between 15 and 20 mg/kg IV Q4W. A maximum dose of 20 mg/kg is selected as the top dose because it is the highest dose evaluated in the prior evinacumab studies.

Part A consists of up to 4 periods: run-in; screening; single-dose open-label treatment and 16-week observation, and a follow-up period (for patients who do not enter Part C). Upon completion of Part A, patients will have the opportunity to continue into Part C (Figure 1).

Figure 1: Study Flow Diagram Part A

Run-in

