Physical Examination				X
Electrocardiogram ³				X
Height				X
Weight		X		X
Adverse Events	X	X	X	X
Tanner Stage				X
Laboratory Testing⁴:				
Hematology		X		X
Blood Chemistry		X		X
Sex Hormones ⁵				X
HbA1c				X
Urine Pregnancy Test ⁶	X	X	X	X
Urinalysis		X		X
TSH				
Hs-CRP				
PK/Drug Concentration and ADA Samples:				
PK/Drug conc. Sample ^{7,8,9}				X
ADA sample ¹⁰				X
Biomarkers:				
Future Biomedical Research Serum				X
Future Biomedical Research Plasma				X
Pharmacogenomics:				
Whole Blood for DNA (optional) ¹¹				
Other				
Review of Diet, compliance with LMT	X	X	X	X
Carotid Ultrasound Imaging				

Table 3: Schedule of Events – Part C

	Treatment Period													24-Week Follow-up Period ¹⁴			
Study Procedure	V1 ¹⁵	V2	V3	V4	V5	V6	V7	V8	V9	V10	V11	V12	V13 EOT ¹⁷	PV 14	V 15	PV 16	EOS V17
	Weeks post last dose																
Week	0	4	8	12	16	20	24	28	32	36	40	44	48	+8	+12	+16	+24
Visit Window (day)		±5	±5	±5	±5	±5	±5	±5	±5	±5	±5	±5	±5	±5	±5	±5	±5
Treatment:																	
Administer Study Drug	X ¹⁶	X	X	X	X	X	X	X	X	X	X	X	X				
Concomitant Meds and Treatment		X	X	X	X	X	X	X	X	X	X	X	X	X	X	X	X
Efficacy:																	
Lipid Panel (fasting): total C, LDL-C, HDL-C, TG, non-HDL-C ¹			X		X		X	X	X	X	X	X	X		X		X
Specialty Lipid Panel (fasting): Apo B, Apo A-1, ApoCIII, ApoE, Lp(a) ¹			X		X		X	X	X	X	X	X	X		X		X
Safety:																	
Vital Signs ²		X	X	X	X	X	X	X	X	X	X	X	X		X		X
Physical Examination													X				X
Electrocardiogram ³													X				X
Tanner Stage ⁴							X						X				X
Height ⁴							X						X				X
Weight		X	X	X	X	X	X	X	X	X	X	X	X				X
Adverse Events		X	X	X	X	X	X	X	X	X	X	X	X	X	X	X	X
Laboratory Testing⁵:																	
Hematology			X		X		X		X		X		X		X		X
Blood Chemistry			X		X		X		X		X		X		X		X
HbA1c				X			X			X			X		X		X
Sex Hormones ^{4,6}							X						X				X
Urine Pregnancy Test ⁷		X	X	X	X	X	X	X	X	X	X	X	X	X	X	X	
Urinalysis			X		X		X		X		X		X				X
Hs-CRP				X			X										X
PK/Drug Concentration and ADA Samples:																	

	Treatment Period													24-Week Follow-up Period ¹⁴			
Study Procedure	V1 ¹⁵	V2	V3	V4	V5	V6	V7	V8	V9	V10	V11	V12	V13 EOT ¹⁷	PV 14	V 15	PV 16	EOS V17
	Weeks post last dose																
Week	0	4	8	12	16	20	24	28	32	36	40	44	48	+8	+12	+16	+24
Visit Window (day)		±5	±5	±5	±5	±5	±5	±5	±5	±5	±5	±5	±5	±5	±5	±5	±5
PK/Drug conc. Sample ^{8,9,10}				X			X			X			X				X
ADA sample ¹¹							X						X				X
Biomarkers:																	
Future Biomedical Research Serum ¹²			X				X						X				X

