14. At weeks 8 and 16 of the follow-up period all patients will be contacted by phone to query LMT compliance, to inquire about AEs or changes to concomitant medications, confirm required contraception use, and remind patients of pregnancy reporting. Sexually active females of childbearing potential will report the results of their home pregnancy test. For patients who decide to enter a compassionate use or early access program, the EOT visit will be their last visit and they will forgo the 24-week follow-up period.
15. Overlapping assessments completed at the EOT visit of Part A or Part B do not need to be duplicated during visit 1 of Part C. Part C visit 1 should occur on the same day as Part A visit 11 or Part B visit 11. All necessary assessments are listed in the applicable SOE (Part A or Part B) column for visit 11.
16. Patient can only receive the dose once all assessments from Part A or Part B Visit 11 are completed.
17. For patients who decide to enter a CUP or EAP, the EOT visit will be their last visit and they will forgo the 24-week follow-up period.

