10.1.2. Data Collection Period

The investigator will record all events, serious and non-serious, that occur from the time of signing the informed consent and for 24 weeks after the last dose of study drug (ie, the follow-up/post treatment period). The follow-up/post treatment period applies to all patients who complete the study or terminate early (excludes those who withdraw consent). However, for those patients entering a CUP or EAP, they may forgo the 24-week follow-up period.

From the time of signing the informed consent and prior to first dose of study drug, the investigator will report the following types of events on the AE CRF:

- SAEs
- Events, serious and non-serious, attributed to study conduct, such as a protocol-mandated procedure or intervention (eg, events related to an invasive procedure such as a biopsy)

Other events that occur prior to the first dose of study drug should be reported on the medical history CRF.

From first dose of study drug, report all AEs on the AE CRF until EOS visit, which includes the follow-up/post treatment period after last dose.

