11.2. Justification of Sample Size

Since this is an open-label single treatment arm study, formal statistical testing is not planned. Therefore, a calculation for patient sample size is not applicable.

Six patients are planned to be enrolled for Part A and 14 pediatric patients are planned to be enrolled for Part B, considering the recruitment constraints in this rare patient population.

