4.6. Study Treatment Exposure and Compliance Variables

Study treatment exposure variables for infusions administered in Part A are listed below with associated definitions:

- The total number of Part A study treatment infusions by patient.
- Patient duration of Part A observation treatment period in weeks defined as: (last visit date during the Part A observation period - first study treatment administration date in Part A)/7.

Study treatment exposure variables for infusions administered in Part B are listed below with associated definitions:

- Patient duration of Part B study treatment exposure in weeks defined as: (last Part B study treatment administration date +28 – first Part B study treatment administration date)/7. Unplanned intermittent discontinuations in study treatment will be addressed on a case-by-case basis, since this is expected to be a rare occurrence. Values will be rounded to one decimal place.
- The total number of Part B study treatment infusions by patient.
- The following categories will be used for treatment exposure at 4 week intervals: ≥ 1 day and < 4 weeks, ≥ 4 weeks and < 8 weeks, ≥ 8 weeks and < 12 weeks, ≥ 12 weeks and < 16 weeks, ≥ 16 weeks and < 20 weeks, ≥ 20 weeks and < 24 weeks, ≥ 24 weeks.

Study treatment exposure variables for infusions administered in Part C are listed below with associated definitions:

- Patient duration of Part C study treatment exposure in weeks defined as: (last Part C study treatment administration date +28 – first Part C study treatment administration date)/7. Unplanned intermittent discontinuations in study treatment will be addressed on a case-by-case basis, since this is expected to be a rare occurrence. Values will be rounded to one decimal place.
- The total number of Part C study treatment infusions by patient.
- The following categories will be used for treatment exposure at 4 week intervals: ≥ 1 day and < 4 weeks, ≥ 4 weeks and < 8 weeks, ≥ 8 weeks and < 12 weeks, ≥ 12 weeks and < 16 weeks, ≥ 16 weeks and < 20 weeks, ≥ 20 weeks and < 24 weeks, ≥ 24 weeks and < 28 weeks, ≥ 28 weeks and < 32 weeks, ≥ 32 weeks and < 36 weeks, ≥ 36 weeks and < 40 weeks, ≥ 40 weeks and < 44 weeks, ≥ 44 weeks and < 48 weeks, ≥ 48 weeks

Study treatment exposure variables on the integrated data pool (Section 2.4) are listed below with associated definitions:

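### For children who leave Part C for a CUP or EAP, adverse events after the end-of-treatment visit are not routinely collected, yet the SAP treats up to 168 days after the last dose as observed

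*Protocol*

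**What the plan says.** **Leaving the study.** The Protocol synopsis (Study Duration) states, for both routes into Part C, that "patients who enter a CUP or EAP may forgo the 24-week follow-up period after the last dose". Section 6.1 adds: "In this situation, the end of treatment (EOT) visit will be their last visit". Table 3 footnotes 14 and 17 are firmer than the permissive wording elsewhere: "the EOT visit will be their last visit and they will forgo the 24-week follow-up period". Section 9.1 explains that the end-of-study assessments can be skipped because, apart from hs-CRP, they match those at EOT.

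**Infusion at the same visit.** In Protocol Table 3 the row "Administer Study Drug" is marked at all 13 Part C treatment visits, including V13, the EOT visit at week 48. The schedule in SAP Appendix 10.7 does the same. Table 3 footnotes 1 and 5 put blood sampling before the infusion.

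**Adverse event recording.** Protocol 10.1.2 normally collects events up to 24 weeks after the last dose: "From first dose of study drug, report all AEs on the AE CRF until EOS visit". The same section lets CUP/EAP patients forgo that period and names no replacement contact.

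**Analysis.** SAP 1.2.4 says the SAP reflects Amendment 1, which predates the waiver. SAP 4.6 computes Part C exposure from "last Part C study treatment administration date +28". SAP 4.8.1 runs the Part C treatment-emergent (TEAE) period to the last Part C dose plus 168 days, and Protocol 11.4.5.1 matches it. Where Kaplan-Meier curves are drawn, SAP 5.8.1 censors patients without an event at the end of that period. No rule covers a child who left at EOT.

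**The concern.** Protocol 3.2.1 gives long-term safety as the purpose of Part C. Amendment 2 was introduced to spare children 24 weeks without drug. That aim does not require event recording to stop on the day of an infusion, since a telephone contact imposes no time off drug. The argument in Section 9.1 compares lists of tests, not timing: EOT samples precede the infusion, while the end-of-study visit falls 24 weeks after the last dose.

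Two things are at stake:

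- **Collection.** New non-serious events, new non-serious events of special interest (an allergic reaction or a transaminase rise, for example) and serious events judged unrelated have no scheduled route into the study data once the child has left. With 20 children planned (6 in Part A, 14 in Part B), one child with a missed event is 1/20, or 5 percentage points, for that event.
- **Analysis.** The SAP would carry such a child as under observation, and event-free, for months after the last contact.

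**Working it through.** There is no power figure to reproduce; Protocol 11.2 states: "Therefore, a calculation for patient sample size is not applicable". The figures that can be reproduced are the stated study durations.

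**1. Last Part C dose implied by the protocol's durations.** Inputs from the synopsis, in weeks: run-in 8, screening 2, Part A 16 or Part B 24, follow-up 24 after the last dose. Let L be the week of the last Part C dose.

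- Part A + Part C: 8 + 2 + 16 + L + 24. L = 48 gives 98; L = 44 gives 94.
- Part B + Part C: 8 + 2 + 24 + L + 24. L = 48 gives 106; L = 44 gives 102.

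The protocol states 98 and 106, so both reproduce with L = 48.

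**2. Last Part C dose implied by the SAP's derived rules.** Study day = 7 × week + 1, so week 44 is day 309 and week 48 is day 337.

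- SAP Appendix 10.2, Table 4 sets follow-up targets for completers at days 365, 393, 421 and 477, for 8, 12, 16 and 24 weeks after the last dose. From day 309: 309 + 56, + 84, + 112, + 168 = 365, 393, 421, 477, an exact match. From day 337 they would be 393, 421, 449 and 505.
- SAP 4.5 defines completion as at least 44 weeks of dosing plus a week 48 visit.
- SAP 2.1 and 2.3 give 48 weeks of treatment and 20 of follow-up: 48 + 20 = 68 = 44 + 24.

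The schedules in both documents and the protocol's totals therefore fit week 48, and the SAP's derived rules fit week 44.

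**3. Time with no scheduled event collection, for a child whose last contact is EOT (day 337).**

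| | Last dose day 337 | Last dose day 309 |
|---|---|---|
| Part C exposure, (last + 28 − first)/7 | (337 + 28 − 1)/7 = 52.0 weeks | (309 + 28 − 1)/7 = 48.0 weeks |
| Credited exposure days after EOT | 337 + 28 − 337 = 28 | 309 + 28 − 337 = 0 |
| TEAE days after EOT | 337 + 168 − 337 = 168 | 309 + 168 − 337 = 140 |

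In the first column, 28 of 364 credited days (7.7%) are unobserved.

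**4. Scale.** The number of CUP/EAP entrants is not stated. Assuming 1 to 20 children, a week-48 last dose gives 28 to 560 unobserved credited days (0.08 to 1.53 patient-years) and 168 to 3,360 unobserved TEAE days. A week-44 last dose gives 0 credited days and 140 to 2,800 TEAE days.

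**5. Which planned summaries are affected.**

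- Event percentages divide patients with the event by patients in the safety set and count repeats once (Protocol 11.4.5.1, SAP 5.8.1). Exposure time does not enter. A percentage is low only if a child's first occurrence of a term falls in the unobserved time.
- Infusion reactions are divided by the number of administrations (SAP 5.8.2), but they are defined as events up to 2 hours after the infusion (Protocol 10.2.4). Vital signs are taken 30 and 60 minutes after it (Table 3 footnote 2). Much of that window lies within the visit.
- Time-to-event curves, if drawn, keep the child at risk for up to 168 days after last contact.
- Disposition: SAP 4.5 would class the child as not completing follow-up, because the last visit is less than 22 weeks after the last dose.

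**The case against.** The strongest answer is that this is a narrow wording gap, affecting an unstated number of children in a purely descriptive analysis, and that part of it depends on an infusion at EOT that the documents do not settle. The SAP predates the waiver and says in its Overview that it may be revised for protocol amendments. Much of this stands, and it rules out three stronger readings.

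- **A reader might infer that nothing is collected after the last infusion.** The documents do not support that. Protocol 10.1.1 keeps drug-related serious events reportable after the reporting period and requires follow-up of serious events and events of special interest until resolved or stable. Section 6.1 covers serious events ongoing at the end, and 10.1.4 covers pregnancies within 24 weeks. The waiver is also mostly worded as an option, although footnotes 14 and 17 are not. CUP/EAP programs may have their own safety reporting, but neither document describes it or brings it into the study data.
- **A reader might infer that event incidence is biased by 7.7%.** It is not. That figure is a share of credited exposure, which feeds a duration summary. The listed event summaries include no exposure-adjusted rate.
- **A reader might take the EOT infusion as settled.** The 98 and 106 weeks are maxima built from nominal periods, and three parts of the SAP fit week 44.

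The objection does not remove the gap. Even with a week-44 last dose, 140 of the 168 TEAE days are unobserved, and the SAP has no rule for them.

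**Conclusion.** The point holds as a cheap improvement to safety capture and to the SAP, not as evidence of a quantified bias. On the current text, a CUP/EAP child is scheduled to be infused at the visit that ends participation, and routine event collection ends with it. If that infusion is given, all 28 credited exposure days and all 168 TEAE days lie beyond last contact. If the last dose is at week 44, 0 and 140 do. Incidence is understated only by events actually missed, and the documents give no basis for estimating how many.

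This rests on EOT falling at day 337 and being the last contact, and on no safety data returning from the CUP/EAP to the study. The number of entrants is unknown; the amendment says only that many physicians are applying or interested. No view is taken on which last-dose week is right.

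**What to change.** 1. **Reconcile the last Part C dose.** Protocol Table 3, SAP Appendix 10.7 and the 98- and 106-week totals must agree with SAP 2.1, 2.3, 4.5 and Appendix 10.2, Table 4.
2. **Keep the 24-week waiver, and close the record.** In the synopsis, Section 6.1, Table 3 footnotes 14 and 17, and Sections 9.1.2 and 10.1.2, state that recording of adverse events, serious events and events of special interest continues until the first CUP/EAP dose or 28 days after the last study infusion, whichever comes first, and ends with one telephone contact. The 28 days are a choice, taken from the SAP's own exposure credit. Nothing is added if EOT already falls at least 28 days after the last infusion.
3. **Amend SAP 4.8.1 and 5.8.1.** For CUP/EAP children, end the TEAE period and any censoring at last study contact, and report how many there are. Protocol 11.4.5.1 needs a matching line. The SAP already truncates the Part A and Part B periods at entry to Part C, so the device is not new.

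Cost: one call per such child, in a part of the study that already uses telephone visits, plus small wording edits. No clinic visit or sample is added, and access to drug is unchanged.

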1. INTRODUCTION

Familial hypercholesterolemia (FH), a primary hyperlipidemia driven by genetic mutation(s) primarily in the low-density lipoprotein (LDL) receptor (LDLR), is the most common monogenic hypercholesterolemia condition in children. The most rare and severe form of FH is homozygous familial hypercholesterolemia (HoFH). It is an inherited autosomal dominant disorder primarily resulting from mutations in the LDLR or, less frequently, from mutations in 3 associated genes: proprotein convertase subtilisin/kexin type 9 (PCSK9), apolipoprotein B (APOB), and LDL receptor adaptor protein 1 (LDLRAP1). Depending on the genes affected and the mutations that are present, patients are categorized as either true homozygotes, compound heterozygotes, or double heterozygotes. True homozygotes have the same mutation on both alleles. Compound heterozygotes have different mutations on the 2 alleles. Double heterozygotes have mutations in 2 different genes. The resulting phenotype includes deficient or defective LDL receptors on the surface of hepatocytes causing impaired clearance of circulating low-density lipoprotein cholesterol (LDL-C). This leads to severe hypercholesterolemia, often 3 to 6 times normal (≥ 500 mg/dL), starting in infancy, which results in an exceedingly high risk of developing premature atherosclerosis, as well as valvular and supravalvular stenosis.

The etiology of the hypercholesterolemia observed in patients with HoFH is the same for both adult and pediatric patients. It is a consequence of the above mentioned abnormal lipoprotein metabolism due to mutations in the key genes listed above, and the markedly diminished hepatic LDL-C clearance from plasma (Goldstein, 2001)(Kolansky, 2008)(Macchiaiolo, 2012) (Rader, 2003). These high plasma levels lead to vascular damage starting from birth and morphological and functional vascular changes by 8 years of age or earlier. Children as young as 7 years of age can present with coronary atherosclerosis even without any clinically apparent coronary artery disease. This accelerated atherosclerosis results in premature cardiovascular disease (CVD) and an increased risk of CV events at a young age. Evidence of accelerated atherosclerosis include children with increased carotid intima-media thickness (cIMT) and cIMT progression at a rate approximately double that of unaffected siblings. An observational study of HoFH patients showed that the mean age for first major CV event was 20 years (Goldstein, 2001)(Kolansky, 2008)(Macchiaiolo, 2012)(Rader, 2003). Indeed, if left untreated, children and adolescents with HoFH, have an extremely high risk for premature CVD and reduced life expectancy. For example, in a longitudinal study of 39 pediatric patients with HoFH followed for up to 8 years, 88% of patients >16 years of age and 9% <16 years of age developed CVD. Further, during follow-up, 7 patients developed progression of coronary and/or aortic valvular disease and 4 required surgical intervention (Kolansky, 2008), demonstrating the need for early aggressive lipid-lowering therapy in pediatric subjects with HoFH.

The frequency of HoFH in the general population is historically reported as 1/1,000,000. This estimate is based on a heterozygous familial hypercholesterolemia (HeFH) prevalence of 1/500 and the application of the Hardy-Weinberg equilibrium ($1/1,000,000 = 1/500$ mother * $1/500$ father * $1/4$ risk for child). However, based on more recent data, HoFH has an estimated prevalence of 1/300,000, which would be the same in children. Populations with a founder effect have higher prevalence rates.

Diagnosis of HoFH can be made based on clinical criteria or genetic criteria (Section 7.2.1). An LDL-C level ≥ 13 mmol/L (≥ 500 mg/dL) is consistent with phenotypic HoFH. However, the LDL-C criteria could be lower depending on the presence of positive family history and age of

screening. Additional phenotypic characteristics include premature coronary heart disease, aortic valve disease, and tendon xanthomas in the hands and Achilles tendons. Clinically identified patients could undergo genetic testing to confirm diagnosis.

Patients with HoFH can be further classified based on the phenotype of the LDLR mutation(s), ranging from defective mutations (where the LDLR retains some LDL-binding functionality) to null or negative mutations where no functioning LDLR is expressed. Patients who have LDLR activity <15% are considered null and patients whose LDLR activity is impaired but >15% are LDLR defective (Banerjee, 2019). Another method that could be used to categorize these mutations is to define a negative mutation status as having mutations in stop codons, frame shifts, splice site changes, small and large insertions/deletions, and copy number variations (CNVs) predicted to result in the loss of function of the LDLR. The most extreme cases are those patients who are LDL-receptor negative or null in both alleles. These patients tend to have LDL-C levels at the highest end of the range and experience very little efficacy from existing therapies such as statins and PCSK9 inhibitors. As such, significantly accelerated atherosclerosis and worse clinical outcomes are observed in these patients compared to those who are LDLR defective (Kolansky, 2008) (Moorjani, 1993). Patients who are LDLR null or negative develop xanthomas sooner than patients who are LDLR receptor defective, and untreated patients who are LDLR null or negative rarely live past the second decade of life (Kolansky, 2008) (Moorjani, 1993).

Current approved therapies for patients with HoFH include statins, lomitapide, ezetimibe, evolocumab, and lipoprotein apheresis. All but lomitapide are approved for use in pediatric patients ≥ 12 years of age. Some of the statins are approved in younger patients (rosuvastatin approved in ages ≥ 6 years; atorvastatin and simvastatin approved for ages ≥ 10 years). Because the etiology of the disease is the same for both adult and pediatric patients, the overarching goal of therapy is also the same, to lower LDL-C. The current American College of Cardiology/American Heart Association (ACC/AHA) guidelines and the European Atherosclerosis Society (EAS) recommend at least a 50% reduction in LDL-C in all patients with FH to reduce the risk of CVD (Gidding, 2015)(Grundy, 2019)(Wiegman, 2015). The EAS further recommends a target LDL-C <130 mg/dl (3.5 mmol/L) in patients >10 years (Wiegman, 2015). Lipid-lowering therapy should be started as early as possible (Cuchel, 2014) (France, 2016) (Wiegman, 2015).

Angiopoietin-like protein 3 (ANGPTL3) has recently emerged as a target for treatment of elevated levels of LDL-C. Individuals who are homozygous for loss of function (LOF) mutations in ANGPTL3 have lower levels of LDL-C (mean difference of >50% versus control subjects (Minicocci, 2012)). The mechanism by which ANGPTL3 LOF mutations result in lowering LDL-C is not fully understood but appears to be independent of the LDLR. These data suggest that inhibiting ANGPTL3 may be a meaningful and well-tolerated strategy for lowering serum LDL-C in patients with HoFH, especially those considered to have LDLR negative mutations in both alleles.

Evinacumab (REGN1500) is a fully human monoclonal antibody (mAb), created with Regeneron's VelocImmune® technology platform, which specifically binds to and inhibits ANGPTL3. In an open-label, single-arm, proof-of-concept study in patients with HoFH (R1500-CL-1331), evinacumab demonstrated a mean percent reduction from baseline of 49.2% (n=9) at week 4, 2 weeks after a single dose of 15 mg/kg IV, with a duration of effect of at least

10 weeks (n=7). A peak mean reduction of 52.1% was observed at week 6. Three patients in the study had null/null mutations in the LDLR. Treatment with evinacumab in these difficult-to-treat patients reduced LDL-C by an average of 37.3% at week 4 with peak reductions up to 59.5%.

The LDL-C lowering effect observed with evinacumab in the R1500-CL-1331 study was confirmed in study R1500-CL-1629, a large randomized, double-blind, placebo-controlled study consisting of adult and adolescent patients with HoFH. On average, patients entered the trial with a mean baseline LDL-C of 255 mg/dL, despite treatment with other lipid-lowering therapies, including maximally-tolerated statins, PCSK9 inhibitors, ezetimibe, LDL apheresis and lomitapide. The trial met its primary endpoint, showing that adding evinacumab to other lipid-lowering therapies decreased LDL-C by a mean of 49% from baseline to week 24, compared to lipid-lowering therapies alone (47% reduction for evinacumab compared to a 2% increase for placebo, $p < 0.0001$). This reduction translates to a mean absolute change in LDL-C of 132 mg/dL from baseline, compared to placebo (135 mg/dL reduction for evinacumab compared to a 3 mg/dL reduction for placebo, $p < 0.0001$). The decreases in LDL-C were observed from the first lipid assessment at week 2 and were maintained throughout the 24-week double-blind treatment period. Importantly, similar levels of LDL-C lowering were observed in the most difficult-to-treat null/null or negative/negative patients. The dramatic reduction in LDL-C led to the achievement of LDL-C levels < 100 mg/dL in 47% of the patients treated with evinacumab compared to 23% treated with placebo (nominal $p = 0.0203$). Evinacumab also reduced apolipoprotein B (Apo B), non-high-density lipoprotein (HDL) cholesterol (non-HDL-C) and total cholesterol (TC) compared to placebo.

The positive efficacy data in the R1500-CL-1629 study were accompanied by an acceptable safety profile. Evinacumab was generally well-tolerated. During the double-blind treatment period, 66% of evinacumab patients and 81% of placebo patients experienced an adverse event (AE). AEs that occurred in at least 5% of patients and more commonly with evinacumab were influenza-like illness (11% evinacumab, 0% placebo) and rhinorrhea (7% evinacumab, 0% placebo). During the double-blind treatment period there was no difference in the incidence of nausea, abdominal pain or diarrhea between treatment groups, and there were no deaths, major adverse cardiovascular events or findings related to hepatic disorders.

The primary purpose of this current study is to demonstrate the efficacy, safety and tolerability of evinacumab in pediatric patients, aged 5 through 11 years, with HoFH. The study will consist of 3 parts: Part A (phase 1b), Part B (phase 3), and Part C (phase 3). Part A is a single-dose, open-label study to determine the safety, pharmacokinetics (PK) and pharmacodynamics (PD) of evinacumab 15 mg/kg intravenous (IV) in approximately 6 patients ages 5 to 11 years with HoFH. Part B is a 24-week, single-arm, open-label study to assess the efficacy and safety of evinacumab in approximately 14 pediatric patients with HoFH. Part B will begin when PK data from all patients in Part A have been sufficiently analyzed to determine the dose for Part B. Part C is an extension of the study available to patients who complete Part A or Part B to continue to receive evinacumab.

Additional background information on the study drug and development program can be found in the Investigator's Brochure.

